### ***Data Collection Tools/Source Data***

An electronic data capture system will be used in this study. The site must define and retain all source records and must maintain a record of any data where source data are directly entered into the data capture system.

### ***Data Protection***

Data systems used for the study will have controls and requirements in accordance with local data protection law.

The purpose and use of patient personal information collected will be provided in a written document to the patient by the sponsor.

### ***Study and Site Closure***

#### ***Discontinuation of Study Sites***

Study site participation may be discontinued if Lilly or its designee, the investigator, or the ERB of the study site judges it necessary for medical, safety, regulatory, or other reasons consistent with applicable laws, regulations, and GCP.

#### ***Discontinuation of the Study***

The study will be discontinued if Lilly or its designee judges it necessary for medical, safety, regulatory, or other reasons consistent with applicable laws, regulations, and GCP.

---

## Appendix 4. Hepatic Monitoring Tests for Treatment-Emergent Abnormality

---

Selected tests may be obtained in the event of a treatment-emergent hepatic abnormality and may be required in follow-up with patients in consultation with Lilly or its designee CRP.

### Hepatic Monitoring Tests

---

#### Hepatic Hematologya

Hemoglobin  
Hematocrit  
RBC  
WBC  
Neutrophils  
Lymphocytes  
Monocytes  
Eosinophils  
Basophils  
Platelets

#### Hepatic Chemistrya

Total bilirubin  
Conjugated bilirubin  
Alkaline phosphatase  
ALT  
AST  
GGT  
CPK

#### Haptoglobina

#### Hepatic Coagulationa

Prothrombin Time  
Prothrombin Time, INR

#### Hepatic Serologiesa,b

Hepatitis A antibody, total  
Hepatitis A antibody, IgM  
Hepatitis B surface antigen  
Hepatitis B surface antibody  
Hepatitis B Core antibody  
Hepatitis C antibody  
Hepatitis E antibody, IgG  
Hepatitis E antibody, IgM

#### Anti-nuclear antibodya

#### Alkaline Phosphatase Isoenzymesa

#### Anti-smooth muscle antibody (or anti-actin antibody)a

Abbreviations: ALT = alanine aminotransferase; AST = aspartate aminotransferase; CPK = creatine phosphokinase; GGT = gamma-glutamyl transferase; Ig = immunoglobulin; INR = international normalized ratio; RBC = red blood cells; WBC = white blood cells.

a Assayed by local laboratory.

b Reflex/confirmation dependent on regulatory requirements and/or testing availability.

---

## Appendix 5. Blood Sampling Summary

---

This table summarizes the approximate number of venipunctures and blood volumes for all blood sampling (screening, safety laboratories, and bioanalytical assays) during the study.

### Protocol H9X-JE-GBGK Sampling Summary

Purpose	Blood Volume per Sample (mL)	Number of Blood Samples	Total Volume (mL)
Hematology, clinical chemistry, endocrinology a	8	5	40
HbA1c	2	4	8
Serology tests	6	1	6
Serum pregnancy test	2	1	2
Fasting blood glucose	2	1	2
MTT (glucose, insulin, c-peptide, glucagon, and triglyceride)	6	56	336
Total			394

Abbreviations: HbA1c = glycated hemoglobin; MTT = meal tolerance test.

a Additional samples may be drawn if needed for safety purposes.

## Appendix 6. Meal Tolerance Test

Time	Procedure
-120 min	Physical exam, vital signs (sitting) Weight (only Day 1, Day 29, Day 57, and Day 85) ECG (only Day 1 and Day 57) Urine sampling for pregnancy test (only Day 1 and Day 57, if needed) Urinalysis and UACR (only Day 1, Day 29, Day 57, and Day 85) Blood sampling for hematology, clinical chemistry, endocrinology, HbA1c (only Day 1, Day 29, Day 57, and Day 85) Blood sampling for glucose, insulin, c-peptide, glucagon, and triglyceride (for 0 min) Satiety evaluation (VAS) (for 0 min)
0 min	Start standardized test meal a
30 min	Blood sampling for glucose, insulin, c-peptide, glucagon, and triglyceride
60 min	Blood sampling for glucose, insulin, c-peptide, glucagon, and triglyceride Satiety evaluation (VAS)
90 min	Blood sampling for glucose, insulin, c-peptide, glucagon, and triglyceride
120 min	Blood sampling for glucose, insulin, c-peptide, glucagon, and triglyceride Satiety evaluation (VAS)
180 min	Blood sampling for glucose, insulin, c-peptide, glucagon, and triglyceride Satiety evaluation (VAS)
240 min	Blood sampling for glucose, insulin, c-peptide, glucagon, and triglyceride Satiety evaluation (VAS)
After MTT	Dose of dulaglutide 0.75 mg or placebo (except Days 29 and 85)

Abbreviations: HbA1c = glycated hemoglobin; min = minutes; MTT = meal tolerance test; UACR = urine albumin/creatinine ratio; VAS = visual analog scale.

a Japanese standard test meal (480 kcal, carbohydrate: protein: fat = 2.8:1:1) should be ingested within 15 min.

---

**Appendix 7. Protocol Amendment H9X-JE-GBGK(a)  
Summary: A Phase 4 Study to Evaluate Glucodynamic  
Effects of Dulaglutide in Japanese Patients with Type 2  
Diabetes Mellitus**

---

## Overview

Protocol H9X-JE-GBGK(a) A Phase 4 Study to Evaluate Glucodynamic Effects of Dulaglutide in Japanese Patients with Type 2 Diabetes Mellitus has been amended. The new protocol is indicated by Amendment (a) and will be used to conduct the study in place of any preceding version of the protocol.

The overall changes and rationale for the changes made to this protocol are as follows:

**Section 7.5.1:**

The detailed method of a hypoglycemic event is added.

**Section 9.2.2.1:**

Pancreatitis adjudication by an independent committee of expert physicians is removed.

**Appendix 2:**

The detailed item of the serum pregnancy test is removed.

**Appendix 6:**

Time window before the meal tolerance test (MTT) is changed .

Minor editorial changes were made for accuracy, consistency and clarity.

## Revised Protocol Sections

**Note:** All deletions have been identified by ~~strikethroughs~~.  
All additions have been identified by the use of underline.

The numbering system used for inclusion and exclusion criteria provides a unique number for each criterion and allows for efficiency in data collection.

In case an amendment to the protocol adds a criterion, that criterion will receive the next available number, regardless of whether it is an inclusion or exclusion criterion.

### 6.2. Exclusion Criteria

[22] Positive human immunodeficiency virus (HIV) antigen and antibody, hepatitis C antibody, hepatitis B surface antigen, or syphilis at Visit 1.

### 7.5. Special Treatment Considerations

#### 7.5.1 Management of Increased Hypoglycemia Risk

If a hypoglycemic event occurs, the patient should record in the study diary the episode and associated symptoms and/or signs, and rescue treatment (if taken).

~~Investigator should use~~ Study site personnel will record information related to hypoglycemia such as start and end date and time of the following episode, hypoglycemia signs and symptoms present. Following definitions and criteria when diagnosing and will be used for categorizing an episode considered to be related to hypoglycemia (the PG values in this section refer to values determined by a laboratory or International Federation of Clinical Chemistry and Laboratory Medicine plasma-equivalent glucose meters and strips) (American Diabetes Association 2005):

#### 9.2.2. Adverse Events of Interest

##### 9.2.2.1. Pancreatitis

~~All AEs of acute or chronic pancreatitis, as well as cases of confirmed lipase or amylase values  $\geq 3 \times$  ULN, will be adjudicated by an independent committee of expert physicians. In addition, AEs of severe or serious abdominal pain of unknown origin will also be submitted to the adjudication committee to assess for possible pancreatitis or other pancreatic disease. Relevant data from patients with acute or chronic pancreatitis, those with severe or serious abdominal pain, and those that undergo additional assessments due to confirmed hyperenzymemia will be entered into a specifically designed CRF page by study site or Lilly staff. The adjudication committee representative will enter the results of adjudication in a corresponding CRF page.~~

### 9.4.2. Vital Signs

Vital signs should be taken before collection of blood samples for laboratory testing. For each parameter, 3 measurements will be taken 1 minute apart using the same arm. An appropriately sized cuff (cuff bladder encircling at least 80% of the upper arm) should be used to ensure the accuracy of blood pressure measurements. The arm used for the blood pressure measurement should be supported at heart level. Each measurement of sitting heart rate and blood pressure is to be recorded in the CRF.

### 9.4.4. Other Tests

#### 9.4.4.1. Continuous Glucose Monitoring

The **CCI** system (**CCI** [www]) will be used for CGM in this study. Continuous Glucose Monitoring will be performed in each study period. Continuous Glucose Monitoring will be initiated on Day -7 (or -6) and Day 50 (or 51) and will last until Day 8 and Day 64.

## Appendix 2. Clinical Laboratory Tests

### Safety Laboratory Tests a

Urine albumin/creatinine ratio (UACR)	Meal tolerance test
	Glucose
Serum pregnancy test [if applicable] b	Insulin
— <del>Follicle stimulating hormone</del>	c-peptide
Urine pregnancy test [if applicable]	Glucagon
	Triglyceride
Serology b	
Hepatitis B surface antigen	Endocrinology
Hepatitis C antibody	Total amylase
HIV antigen and antibody	Lipase
Syphilis	Calcitonin

Abbreviations: HIV = human immunodeficiency virus; HbA1c = glycated hemoglobin; RBC = red blood cells; WBC = white blood cells.

a Assayed by local laboratory.

b Performed at screening only.

**Appendix 5. Blood Sampling Summary****Protocol H9X-JE-GBGK Sampling Summary**

Purpose	Blood Volume per Sample (mL)	Number of Blood Samples	Total Volume (mL)
Hematology, clinical chemistry, endocrinology a	8	5	40
HbA1c	2	4	8
Serology tests	<del>56</del>	1	<del>56</del>
Serum pregnancy test	2	1	2
Fasting blood glucose	2	1	2
MTT (glucose, insulin, c-peptide, glucagon, and triglyceride)	6	56	336
Total			<del>393</del> 394

Abbreviations: HbA1c = glycated hemoglobin; MTT = meal tolerance test.

a Additional samples may be drawn if needed for safety purposes.

**Appendix 6. Meal Tolerance Test**

Time	Procedure
<del>-120 min</del>	Physical exam, vital signs (sitting)
<del>-60 min</del>	Weight (only Day 1, Day 29, Day 57, and Day 85) ECG (only Day 1 and Day 57)
	Urine sampling for pregnancy test (only Day 1 and Day 57, if needed) Urinalysis and UACR (only Day 1, Day 29, Day 57, and Day 85)
	Blood sampling for hematology, clinical chemistry, endocrinology, HbA1c (only Day 1, Day 29, Day 57, and Day 85)
	Blood sampling for glucose, insulin, c-peptide, glucagon, and triglyceride (for 0 min) Satiety evaluation (VAS) (for 0 min)

Abbreviations: HbA1c = glycated hemoglobin; min = minutes; MTT = meal tolerance test; UACR = urine albumin/creatinine ratio; VAS = visual analog scale.

2. ABBREVIATIONS

Abbreviations pertain to the Statistical Analysis Plan (SAP) only (not the tables, figures and listings [TFLs]).

AE	Adverse event
ALP	Alkaline phosphatase
ALT	Alanine aminotransferase
AUC	Area under the concentration versus time curve
CGM	Continuous glucose monitoring
CI	Confidence interval
CL/F	Apparent total body clearance of drug calculated after extra-vascular administration
CRF	Case Report Form
CSR	Clinical Study Report
CRU	Clinical Research Unit
CV	Coefficient of variation
EC	Early Clinical
ECG	Electrocardiogram
e.g.	For example (Latin: exempli gratia)
iAUC	Incremental AUC
ICH	International Council on Harmonisation
LS	Least square
MedDRA	Medical Dictionary for Regulatory Activities
MRE	Magnetic resonance elastography
MTT	Meal tolerance test
NA	Not applicable
PD	Pharmacodynamic
QW	Once weekly
SAP	Statistical Analysis Plan
SD	Standard deviation
SOP	Standard Operating Procedure
TBL	Total bilirubin

T2D	Type 2 diabetes mellitus
TFLs	Tables, Figures, and Listings
ULN	Upper limit of normal
VAS	Visual analogue scale
WHO	World Health Organization

3. INTRODUCTION

This SAP has been developed after review of the Clinical Study Protocol (final version dated 12 July 2017).

This SAP describes the planned analysis of the safety, tolerability and pharmacodynamic (PD) data from this study. A detailed description of the planned TFLs to be presented in the clinical study report (CSR) is provided in the accompanying TFL shell document.

The intent of this document is to provide guidance for the statistical and PD analyses of data. In general, the analyses are based on information from the protocol, unless they have been modified by agreement between Eli Lilly and Company and Covance Early Clinical (EC) Biometrics. A limited amount of information concerning this study (e.g., objectives, study design) is given to help the reader's interpretation. This SAP must be signed off prior to first patient administration for this study. When the SAP and TFL shells are agreed upon and finalized, they will serve as the template for this study's CSR.

This SAP supersedes the statistical considerations identified in the protocol; where considerations are substantially different, they will be so identified. If additional analyses are required to supplement the planned analyses described in this SAP, they may be performed and will be identified in the CSR. Any substantial deviations from this SAP will be agreed upon between Eli Lilly and Company and Covance EC Biometrics and identified in the CSR. Any minor deviations from the TFLs may not be documented in the CSR.

This SAP is written with consideration of the recommendations outlined in the International Council on Harmonisation (ICH) E9 Guideline entitled Guidance for Industry: Statistical Principles for Clinical Trials¹ and the ICH E3 Guideline entitled Guidance for Industry: Structure and Content of Clinical Study Reports².

4. STUDY OBJECTIVES

4.1 Primary Objective

The primary objective of this study is

- To evaluate glucodynamic effects of dulaglutide 0.75 mg compared with placebo in area under the glucose concentration versus time curve from 0 to 4 hours (glucose AUC[0-4h]) at 4 weeks in Japanese patients with type 2 diabetes mellitus (T2D).

4.2 Secondary Objectives

The secondary objectives of this study are:

- To evaluate PD effects of dulaglutide 0.75 mg compared with placebo at 4 weeks.
- To evaluate safety and tolerability of dulaglutide 0.75 mg for 4 weeks.

4.3 Tertiary/Exploratory Objectives

The exploratory objectives are:

- To evaluate daily glucose variability.
- To evaluate satiety after standardized test meal.

5. STUDY DESIGN

This study is a Phase 4, single-center, randomized, cross-over, single-blind, placebo-controlled study to evaluate glucodynamic effects of dulaglutide after a standardized test meal in Japanese patients with T2D.

[figure not shown]
The study includes a 10- to 28-day screening period, a 4-week treatment period (Period 1), a 4- to 6-week washout period, and a 4-week treatment period (Period 2).

Screening tests will be performed at Visit 1. After confirming eligibility, the patient will be randomized in a 1:1 ratio to dulaglutide 0.75 mg or placebo treatment in Period 1.

Meal tolerance test (MTT) will be performed at baseline, 1, 2, and 4 weeks for each period. Time points for blood sampling will be 0, 30, 60, 90, 120, 180, and 240 minutes after the start of standardized test meal. Satiety will be also assessed at 0, 60, 120, 180, and 240 minutes after the start of standardized test meal. After completion of Period 1, all patients must have a 4- to 6-week washout period, and then will start Period 2 on the opposite treatment (patients taking dulaglutide will be switched to placebo and patients taking placebo will be switched to dulaglutide).

This is a single-blind study, and the treatment assignments will be blinded to patients until study completion.

Figure 1 illustrates the study design.

Abbreviations: CGM = continuous glucose monitoring; dula = dulaglutide; n = number of patients.

Figure 1. General Study Design

6. TREATMENTS

The following is a list of the study treatment abbreviations that will be used in the TFLs.

Study Treatment Name	Treatment order in TFL
Placebo QW	1
0.75 mg dulaglutide QW	2

QW = once weekly

7. SAMPLE SIZE JUSTIFICATION

Up to 14 patients may be entered to randomize 12 patients and complete at least 11 patients. Patients will be randomized in a 1:1 ratio to one of two sequences. Assuming one dropout, the sample size of 11 patients would provide 93% power to demonstrate superiority of dulaglutide to placebo. This computation assumes the true treatment difference in glucose AUC(0-4h) is 190 mg*hr/dL, a common standard deviation of 140 mg*hr/dL, intra-patient correlation of 0.3, and a one-sided significance level of 0.025.

Patients who are randomized but do not complete study treatment may be replaced at the discretion of the investigator and Lilly clinical pharmacologist.

8. DEFINITION OF ANALYSIS POPULATIONS

The “Safety” population will consist of all patients who received at least one dose of study drug (dulaglutide or placebo), and have at least one postdose safety assessment.

The “Pharmacodynamic” population will consist of all patients who received at least one dose of study drug (dulaglutide or placebo), and have evaluable pharmacodynamic data.

All protocol deviations that occur during the study will be considered for their severity/impact and will be taken into consideration when patients are assigned to analysis populations.

9. STATISTICAL METHODOLOGY

9.1 General

Data listings will be provided for all data that is databased. Summary statistics and statistical analysis will only be presented for data where detailed in this SAP. For continuous data, summary statistics will include the arithmetic mean, arithmetic standard deviation (SD), median, min, max and N; for log-normal data the geometric mean and geometric coefficient of variation (CV%) will also be presented. For categorical data, frequency count and percentages will be presented. Data listings will be provided for all patients up to the point of withdrawal, with any patients excluded from the relevant population highlighted. Summary statistics and statistical analyses will generally only be performed for patients included in the relevant analysis population. For the calculation of summary statistics and statistical analysis, unrounded data will be used.

Mean change from baseline is the mean of all individual patients’ change from baseline values. Each individual change from baseline will be calculated by subtracting the individual patient’s baseline value from the value at the timepoint. The individual patient’s change from baseline values will be used to calculate the mean change from baseline using a SAS procedure such as Proc Univariate.

Data analysis will be performed using SAS® Version 9.3 or greater.

9.2 Demographics and Patient Disposition

Patient disposition will be listed. The demographic variables age, sex, race, ethnicity, body weight, height, body mass index, duration of diabetes, screening HbA1c and fasting blood glucose will be summarized and listed.

9.3 Pharmacodynamic Assessment

9.3.1 Pharmacodynamic Analysis

The baseline for all PD parameters is defined as the premeal value on Day 1 for the relevant period.

Primary Measure

The primary measure of PD is the change from baseline in glucose AUC(0-4h) at 4 weeks.

Secondary Measures

The following secondary measures of PD will be evaluated:

- The change from baseline in fasting blood glucose at 1, 2, and 4 weeks
- The change from baseline in postprandial blood glucose (30, 60, 90, 120, 180, and 240 minutes) at 1, 2, and 4 weeks
- The change from baseline in glucose AUC(0-4h) at 1 and 2 weeks
- The change from baseline in insulin (30, 60, 90, 120, 180, and 240 minutes) at 1, 2, and 4 weeks
- The change from baseline in insulin AUC(0-4h) at 1, 2, and 4 weeks
- The change from baseline in C-peptide (30, 60, 90, 120, 180, and 240 minutes) at 1, 2, and 4 weeks
- The change from baseline in C-peptide AUC(0-4h) at 1, 2, and 4 weeks
- The change from baseline in glucagon (30, 60, 90, 120, 180, and 240 minutes) at 1, 2, and 4 weeks
- The change from baseline in glucagon AUC(0-4h) at 1, 2, and 4 weeks
- The change from baseline in triglyceride (30, 60, 90, 120, 180, and 240 minutes) at 1, 2, and 4 weeks
- The change from baseline in triglyceride AUC(0-4h) at 1, 2, and 4 weeks

PD AUCs will be calculated for glucose, insulin, glucagon, c-peptide, and triglyceride data following the standardized test meal at Weeks 0, 1, 2, and 4. The AUC(0-4h) will be calculated using the linear-trapezoidal method and actual times. This analysis will be performed for both original data and adjusted data with the predose value at each period, i.e. incremental AUC (iAUC). The parameters AUC(0-1h), AUC(0-2h), and AUC(0-3h) will also be calculated for glucose, insulin, C-peptide, glucagon and triglyceride together with the corresponding iAUCs.

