9.3.2 Pharmacodynamic Statistical Methodology

All PD parameters will be listed and summarized by treatment group and week. Individual observed and changes from baseline in glucose, insulin, glucagon, C-peptide, and triglyceride concentrations will be listed and summarized and their mean time profiles will be plotted by treatment group together with changes from baseline.

PD AUCs and iAUCs on Weeks 0, 1, 2, and 4 will be analyzed using a mixed-effects linear model for glucose, insulin, glucagon, C-peptide, and triglyceride . The model will include

treatment, sequence, period, week and treatment-by-week interaction as fixed effects, baseline as a covariate and patient as random effect.

The least squares means and the 95% CIs by treatment group will be tabulated and plotted. Comparisons between dulaglutide and placebo will be performed. Difference of least squares means of dulaglutide to placebo, and the 95% CIs, will be tabulated. Example SAS code is given below:

```
proc mixed data=pd;
class patient treatment sequence period week;
model pd = baseline treatment sequence period week treatment*week / ddfm=kr;
repeated week(treatment) / subject=patient type=un;
lsmeans treatment*week / pdiff alpha=0.05;
run;
```

The repeated patient effect models the within-patient errors using an unstructured variance-covariance matrix. If the analysis fails to converge, the following variance-covariance matrix will be used (in order) until one converges:

1. compound symmetry,
2. banded, and then
3. first-order autoregressive.

Continuous plasma glucose monitoring (CGM)

For the CGM data, parameters will be derived from the raw data collected through Day -1 to Day 6 (7 days), of CGM device use by patient and treatment.

The following notation will be used in the definition:

- n represents the number of time points within a day
- i represents a time point within a day
- m represents a day

Within-day glucose SD:

$$SD_m = \sqrt{\frac{\sum_{i=1}^n (BG_i - \left\{ \frac{\sum_{i=1}^n BG_i}{n} \right\})^2}{n-1}}$$

Mean amplitude of glycemic excursions (MAGE):

this parameter is calculated based on the arithmetic mean of differences between consecutive peaks and nadirs of differences greater than one SD of mean glycemia. Mean of the differences between consecutive peaks and nadirs in BG that meet qualifying criteria

$$MAGE_m = \frac{\sum_{l=1}^p |BG_l - BG_{l-h}|}{p}$$

where,

x_l = the low point in consecutive BG time points for the M^{th} day (nadir)

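### SAP 9.3.1 makes the Day 1 premeal value the baseline for every PD parameter, so postprandial changes absorb the meal excursion and the AUC change and covariate use the wrong quantity

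*SAP*

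**What the plan says.** SAP 9.3.1 gives one baseline rule: "The baseline for all PD parameters is defined as the premeal value on Day 1 for the relevant period". SAP 9.1 gives the arithmetic: "Each individual change from baseline will be calculated by subtracting the individual" patient's baseline from the value at the time point.

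The rule then meets three kinds of measure in SAP 9.3.1: fasting glucose, concentrations of five analytes at 30 to 240 minutes, and AUC(0-4h) of the same five. On the primary: "The primary measure of PD is the change from baseline in glucose AUC(0-4h) at 4 weeks". AUCs are calculated for "data following the standardized test meal at Weeks 0, 1, 2, and 4", so a Week 0 AUC exists in each period, but no section names it as the baseline. Nor does any section name the Week 0 value at the same time point.

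SAP 9.3.2 orders the outputs. For concentrations: "Individual observed and changes from baseline in glucose, insulin, glucagon, C-peptide, and triglyceride concentrations will be listed and summarized", with mean profiles of the changes plotted by treatment. For AUCs: "PD AUCs and iAUCs on Weeks 0, 1, 2, and 4 will be analyzed using a mixed-effects linear model", with terms "treatment, sequence, period, week and treatment-by-week interaction as fixed effects, baseline as a covariate and patient as random effect".

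Protocol 10.3.3.2 words the baseline as the Day 1 predose value. In Protocol Appendix 6 the dose follows the meal test, so the whole Week 0 test is predose. SAP section 3 says the SAP supersedes the protocol, and SAP section 11 declares no changes.

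**The concern.** A premeal value is one fasting concentration per analyte and period. It is the right baseline for later premeal concentrations and for nothing else on the list of changes. Used literally, it has three effects:

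1. The change in glucose AUC(0-4h), the primary measure, subtracts mg/dL from mg·hr/dL.
2. Each postprandial change has consistent units but includes the ordinary rise after the Week 0 meal. Showing postprandial effect is the stated purpose of the study (Protocol 3.1), so these are central outputs.
3. The model for AUCs and iAUCs adjusts for a fasting concentration and not for the Week 0 AUC or iAUC, which may cost precision.

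The authors probably meant the corresponding Day 1 value. But a programmer following the text would use the fasting value, and the model's retention of Week 0 among the responses points the same way: a Week 0 AUC covariate would be both response and predictor.

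**Working it through.** **The plan's own figure.** SAP section 7 gives difference 190, SD 140, correlation 0.3, 11 completers and one-sided 0.025. SE of the within-patient contrast = sqrt(2 × 140² × (1 − 0.3) / 11) = 49.95, and 190 / 49.95 = 3.80. The noncentral t gives power 92.8% with 10 df and 92.2% with 9 df, so the stated 93% is reproduced. It does not use the baseline definition.

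**Count.** Measures in SAP 9.3.1: fasting glucose 3 (one per week), postprandial 5 × 6 × 3 = 90, AUC 5 × 3 = 15, total 108. The premeal value is the same parameter in 3. Concentration changes under SAP 9.3.2: 5 × 7 × 3 = 105, of which 5 × 3 = 15 are premeal and 90 are not.

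**Postprandial changes.** For Week w and time t:

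G(w, t) − G(Day 1, 0) = [G(w, t) − G(Week 0, t)] + [G(Week 0, t) − G(Day 1, 0)].

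The second bracket is the Week 0 meal excursion. The documents give no profile, so assume 150, 190, 230, 235, 220, 185, 160 mg/dL at 0, 0.5, 1, 1.5, 2, 3, 4 h, no change on placebo, and a uniform fall of 190 / 4 = 47.5 mg/dL on dulaglutide.

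| Minutes | 30 | 60 | 90 | 120 | 180 | 240 |
|---|---|---|---|---|---|---|
| Placebo, true change | 0 | 0 | 0 | 0 | 0 | 0 |
| Placebo, SAP rule | +40 | +80 | +85 | +70 | +35 | +10 |
| Dulaglutide, true change | −47.5 | −47.5 | −47.5 | −47.5 | −47.5 | −47.5 |
| Dulaglutide, SAP rule | −7.5 | +32.5 | +37.5 | +22.5 | −12.5 | −37.5 |

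The difference between arms is −47.5 throughout. Scaling the excursion by 0.5, 1 or 1.5 makes the dulaglutide sign wrong at 0, 3 or 5 of the 6 times.

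**AUC change.** The linear-trapezoid AUC of the profile is 85 + 105 + 116.25 + 113.75 + 202.5 + 172.5 = 795; with the fall it is 795 − 190 = 605. The literal rule gives 795 − 150 = +645 on placebo (true 0) and 605 − 150 = +455 on dulaglutide (true −190). The difference is −190 either way. Without assuming a profile: if mean post-meal glucose is not below fasting level F, AUC minus F is at least 4F − F = 3F. Over the screening range of 120 to 200 mg/dL (inclusion criterion 4) that is +360 to +600 with no drug effect, or 1.9 to 3.2 times the assumed 190.

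**Covariate.** A 2×2 crossover was simulated with 6 + 5 patients, SD 140, cross-period correlation 0.3, assumed effects 0, −120, −160 and −190 at Weeks 0, 1, 2 and 4, the SAP fixed effects, a random patient intercept (compound symmetry) and 2000 runs per setting. The within-period and premeal-to-AUC correlations are assumptions. SD of the Week 4 contrast:

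| Premeal-to-AUC correlation | Within-period correlation | Premeal covariate, Weeks 0, 1, 2, 4 | Week 0 AUC covariate, Weeks 1, 2, 4 | Ratio |
|---|---|---|---|---|
| 0.8 | 0.5 | 50.7 | 48.8 | 1.04 |
| 0.8 | 0.7 | 46.7 | 41.2 | 1.13 |
| 0.8 | 0.85 | 41.5 | 31.3 | 1.32 |
| 0.6 | 0.5 | 50.7 | 49.3 | 1.03 |
| 0.6 | 0.7 | 48.7 | 42.8 | 1.14 |
| 0.6 | 0.85 | 47.6 | 31.2 | 1.53 |

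The mean contrast was −188 to −191 in every setting. A model using Week 4 alone gave a loss of 0% to 41%.

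As an analytic check on the Week 0 AUC column, with within-period correlation r the within-patient differences in Week 0 and Week 4 AUC correlate at c = (r − 0.3) / 0.7, and SD = 49.95 × sqrt(1 − c²). This gives 47.9, 41.0 and 30.9 for r = 0.5, 0.7 and 0.85, close to the simulation.

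**The case against.** The strongest points on the other side are these.

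- **The inference is sound.** The objective is a comparison with placebo. The excursion has the same expectation in both arms, so the contrast is unbiased, and a fasting covariate is valid. This stands in full.
- **No AUC change table is ordered.** SAP 9.1 says "Summary statistics and statistical analysis will only be presented for data where detailed in this SAP", the SAP text does not explicitly call for AUC changes to be tabulated, and the TFL shells are not available. This stands: the +645 and +455 show what the definition means, not what a known table will contain. The primary measure is still defined as that change.
- **The iAUC already gives a unit-consistent AUC relative to premeal.** True. Subtracting 4 × 150 = 600 in the assumed profile gives +195 and +5, again differing by −190. But iAUC is a separate parameter, not the stated primary, and its own change from baseline still needs a Week 0 iAUC.
- **Predose may have meant premeal in the protocol too.** Protocol 10.3.3.1 uses the predose value to adjust the data, and Protocol 10.3.3.2 keeps Week 0 as a response. So an undeclared change from the protocol is possible but not proven. The defect in the SAP is the same under either reading.
- **The precision loss is speculative.** It rests on assumed correlations, uses the SAP's first fallback covariance and not the unstructured one, and compares with a model nobody planned. Against the planned SE of 49.95, the premeal-covariate SDs of 41.5 to 50.7 are no more than 2% worse. This stands: the loss is precision forgone, not a shortfall against the plan.
- **Week 0 is summarized anyway,** so a reader could recover the true change in means. That softens the harm but does not correct the change summaries and plots.

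**Conclusion.** The concern holds as written. This is a stated rule that gives a wrong result, not a missing detail. The certain part is algebraic: 90 of the 105 concentration changes carry the Week 0 meal excursion, and the primary change is dimensionally inconsistent. How far the within-arm glucose changes mislead depends on the assumed profile. In the central case placebo appears to rise by up to 85 mg/dL and dulaglutide has the wrong sign at half of the postprandial times.

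The SD of the Week 4 contrast would be 3% to 53% larger than with a Week 0 AUC covariate under the assumed correlations, and as little as 0% in the Week-4-only model, so the loss may be negligible or material. The treatment contrast and the 93% power are untouched. It should be fixed, but it does not threaten the primary comparison.

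**What to change.** Replace the baseline sentence in SAP 9.3.1 with a parameter-specific one, for example:

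> Baseline is the value of the same parameter from the Day 1 (Week 0) predose meal test of the relevant period: the Week 0 AUC or iAUC over the same interval for AUCs and iAUCs, the Week 0 value at the same nominal time for each postprandial time point, and the Week 0 premeal value for fasting measures.

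Use it both for change from baseline and as the model covariate. It follows that the SAP 9.3.2 model responses should be limited to Weeks 1, 2 and 4, so that the Week 0 AUC is not both response and covariate. Keep Week 0 in the listings, summaries and plots. With this covariate the Week 4 difference in LS means equals the treatment difference in change from baseline (in the simulation the two agreed to within 3 × 10⁻¹⁰), so the existing LSMEANS statement delivers the primary measure.

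Limiting the weeks is an analysis change, because Protocol 10.3.3.2 and SAP 9.3.2 both name Weeks 0, 1, 2 and 4. Record it in SAP section 11 together with the baseline definition.

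The cost is small: one sentence, an edit to the model text and code, and the matching derivations. No new data are needed. Dropping Week 0 from the responses costs almost nothing in itself: with the premeal covariate kept, the SD moved from 50.7 to 50.0, 46.7 to 46.6 and 41.5 to 41.6 (premeal-to-AUC correlation 0.8).
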